7.2.3 Immediate Reporting of Adverse Events to the Sponsor and to Merck

7.2.3.1 Serious Adverse Events

A serious adverse event is any adverse event occurring at any dose or during any use of Merck's product that:

- Results in death;
- Is life threatening;
- Results in persistent or significant disability/incapacity;
- Results in or prolongs an existing inpatient hospitalization;
- Is a congenital anomaly/birth defect;
- Is a new cancer (that is not a condition of the study);
- Is associated with an overdose;
- Is another important medical event

Refer to Table 6 for additional details regarding each of the above criteria.

Any serious adverse event, or follow up to a serious adverse event, including death due to any cause other than progression of the cancer under study that occurs to any subject from the time the consent is signed through 90 days following cessation of treatment, or the initiation of new anti-cancer therapy, whichever is earlier, whether or not related to Merck product, must be reported within 24 hours to the Sponsor and within 2 working days to Merck Global Safety.

Non-serious Events of Clinical Interest will be forwarded to Merck Global Safety and will be handled in the same manner as SAEs.

Additionally, any serious adverse event, considered by an investigator who is a qualified physician to be related to Merck product that is brought to the attention of the investigator at any time outside of the time period specified in the previous paragraph also must be reported immediately to the Sponsor and to Merck.

SAE reports and any other relevant safety information are to be forwarded to the Merck Global Safety [contact]

A copy of all 15 Day Reports and Annual Progress Reports is submitted as required by FDA, European Union (EU), Pharmaceutical and Medical Devices agency (PMDA) or other local regulators. Investigators will cross reference this submission according to local regulations to the Merck Investigational Compound Number (IND, CSA, etc.) at the time of submission. Additionally investigators will submit a copy of these reports to Merck & Co., Inc. (Attn: Worldwide Product Safety; [contact]) at the time of submission to FDA.

All subjects with serious adverse events must be followed up for outcome.

7.2.3.2 Events of Clinical Interest

Selected non-serious and serious adverse events are also known as Events of Clinical Interest (ECI) and must be recorded as such on the Adverse Event case report forms/worksheets and reported within 24 hours to the Sponsor and within 2 working days to Merck Global Safety. (Attn: Worldwide Product Safety; [contact]) Events of clinical interest for this trial include:

1. an overdose of Merck product, as defined in Section 7.2.1 - Definition of an Overdose for This Protocol and Reporting of Overdose to the Sponsor, that is not associated with clinical symptoms or abnormal laboratory results.
2. an elevated AST or ALT lab value that is greater than or equal to 3X the upper limit of normal and an elevated total bilirubin lab value that is greater than or equal to 2X the upper limit of normal and, at the same time, an alkaline phosphatase lab value that is less than 2X the upper limit of normal, as determined by way of protocol-specified laboratory testing or unscheduled laboratory testing.*

*Note: These criteria are based upon available regulatory guidance documents. The purpose of the criteria is to specify a threshold of abnormal hepatic tests that may require an additional evaluation for an underlying etiology. The trial site guidance for assessment and follow up of these criteria can be found in the Investigator Trial File Binder (or equivalent).

1. Additional adverse events:

A separate guidance document has been provided entitled “Event of Clinical Interest Guidance Document” (previously entitled, “Event of Clinical Interest and Immune-Related Adverse Event Guidance Document”). This document can be found in Appendix 4 and provides guidance regarding identification, evaluation and management of ECIs and irAEs.

ECIs (both non-serious and serious adverse events) identified in this guidance document from the date of first dose through 90 days following cessation of treatment, or 30 days after the initiation of a new anticancer therapy, whichever is earlier, need to be reported within 24 hours to the Sponsor and within 2 working days to Merck Global Safety. (Attn: Worldwide Product Safety; [contact]), regardless of attribution to study treatment, consistent with standard SAE reporting guidelines.

Subjects should be assessed for possible ECIs prior to each dose. Lab results should be evaluated and subjects should be asked for signs and symptoms suggestive of an immune-related event. Subjects who develop an ECI thought to be immune-related should have additional testing to rule out other etiologic causes. If lab results or symptoms indicate a possible immune-related ECI, then additional testing should be performed to rule out other etiologic causes. If no other cause is found, then it is assumed to be immune-related.

7.2.4 Evaluating Adverse Events

An investigator who is a qualified physician will evaluate all adverse events according to the NCI Common Terminology for Adverse Events (CTCAE), version 4.0. Any adverse event which changes CTCAE grade over the course of a given episode will have each change of grade recorded on the adverse event case report forms/worksheets.

All adverse events regardless of CTCAE grade must also be evaluated for seriousness.

Table 6 Evaluating Adverse Events

An investigator who is a qualified physician, will evaluate all adverse events as to:

V4.0 CTCAE Grading	Grade 1	Mild; asymptomatic or mild symptoms; clinical or diagnostic observations only; intervention not indicated.
	Grade 2	Moderate; minimal, local or noninvasive intervention indicated; limiting age-appropriate instrumental ADL.
	Grade 3	Severe or medically significant but not immediately life-threatening; hospitalization or prolongation or hospitalization indicated; disabling; limiting self-care ADL.
	Grade 4	Life threatening consequences; urgent intervention indicated.
	Grade 5	Death related to AE
Seriousness	
A serious adverse event is any adverse event occurring at any dose or during any use of Merck product that:
 
†Results in death; or
 
†Is life threatening; or places the subject, in the view of the investigator, at immediate risk of death from the event as it occurred (Note: This does not include an adverse event that, had it occurred in a more severe form, might have caused death.); or
 
†Results in a persistent or significant disability/incapacity (substantial disruption of one’s ability to conduct normal life functions); or
 
†Results in or prolongs an existing inpatient hospitalization (hospitalization is defined as an inpatient admission, regardless of length of stay, even if the hospitalization is a precautionary measure for continued observation. (Note: Hospitalization [including hospitalization for an elective procedure] for a preexisting condition which has not worsened does not constitute a serious adverse event.); or
 
†Is a congenital anomaly/birth defect (in offspring of subject taking the product regardless of time to diagnosis); or
 
Is a new cancer; (that is not a condition of the study) or
 
Is an overdose (whether accidental or intentional). Any adverse event associated with an overdose is considered a serious adverse event. An overdose that is not associated with an adverse event is considered a non-serious event of clinical interest and must be reported within 24 hours.
 
Other important medical events that may not result in death, not be life threatening, or not require hospitalization may be considered a serious adverse event when, based upon appropriate medical judgment, the event may jeopardize the subject and may require medical or surgical intervention to prevent one of the outcomes listed previously (designated above by a †).
	
Duration	Record the start and stop dates of the adverse event. If less than 1 day, indicate the appropriate length of time and units	
Action taken	Did the adverse event cause the Merck product to be discontinued?	

Relationship to test drug	
Did the Merck product cause the adverse event? The determination of the likelihood that the Merck product caused the adverse event will be provided by an investigator who is a qualified physician. The investigator's signed/dated initials on the source document or worksheet that supports the causality noted on the AE form, ensures that a medically qualified assessment of causality was done. This initialed document must be retained for the required regulatory time frame. The criteria below are intended as reference guidelines to assist the investigator in assessing the likelihood of a relationship between the test drug and the adverse event based upon the available information.
 
The following components are to be used to assess the relationship between the Merck product and the AE; the greater the correlation with the components and their respective elements (in number and/or intensity), the more likely the Merck product caused the adverse event (AE):
	
	Exposure	Is there evidence that the subject was actually exposed to the Merck product such as: reliable history, acceptable compliance assessment (pill count, diary, etc.), expected pharmacologic effect, or measurement of drug/metabolite in bodily specimen?
	Time Course	Did the AE follow in a reasonable temporal sequence from administration of the Merck product? Is the time of onset of the AE compatible with a drug-induced effect (applies to trials with investigational medicinal product)?
	Likely Cause	Is the AE not reasonably explained by another etiology such as underlying disease, other drug(s)/vaccine(s), or other host or environmental factors

Relationship to Merck product (continued)	The following components are to be used to assess the relationship between the test drug and the AE: (continued)	
	Dechallenge	
Was the Merck product discontinued or dose/exposure/frequency reduced? If yes, did the AE resolve or improve? If yes, this is a positive dechallenge. If no, this is a negative dechallenge. (Note: This criterion is not applicable if: (1) the AE resulted in death or permanent disability; (2) the AE resolved/improved despite continuation of the Merck product; or (3) the trial is a single-dose drug trial); or (4) Merck product(s) is/are only used one time.)

	Rechallenge	
Was the subject re-exposed to the Merck product in this study? If yes, did the AE recur or worsen? If yes, this is a positive rechallenge. If no, this is a negative rechallenge. (Note: This criterion is not applicable if: (1) the initial AE resulted in death or permanent disability,

		or (2) the trial is a single-dose drug trial); or (3) Merck product(s) is/are used only one time). NOTE: IF A RECHALLENGE IS PLANNED FOR AN ADVERSE EVENT WHICH WAS SERIOUS AND WHICH MAY HAVE BEEN CAUSED BY THE MERCK PRODUCT, OR IF REEXPOSURE TO THE MERCK PRODUCT POSES ADDITIONAL POTENTIAL SIGNIFICANT RISK TO THE SUBJECT, THEN THE RECHALLENGE MUST BE APPROVED IN ADVANCE BY THE U.S. CLINICAL MONITOR AS PER DOSE MODIFICATION GUIDELINES IN THE PROTOCOL.
	Consistency with Trial Treatment Profile	Is the clinical/pathological presentation of the AE consistent with previous knowledge regarding the Merck product or drug class pharmacology or toxicology?
The assessment of relationship will be reported on the case report forms /worksheets by an investigator who is a qualified physician according to his/her best clinical judgment, including consideration of the above elements.		
Record one of the following	Use the following scale of criteria as guidance (not all criteria must be present to be indicative of a Merck product relationship).	
Yes, there is a reasonable possibility of Merck product relationship.	There is evidence of exposure to the Merck product. The temporal sequence of the AE onset relative to the administration of the Merck product is reasonable. The AE is more likely explained by the Merck product than by another cause.	
No, there is not a reasonable possibility of Merck product relationship	Subject did not receive the Merck product OR temporal sequence of the AE onset relative to administration of the Merck product is not reasonable OR there is another obvious cause of the AE. (Also entered for a subject with overdose without an associated AE.)	

7.2.5 Sponsor Responsibility for Reporting Adverse Events

All Adverse Events will be reported to regulatory authorities, IRB/IECs and investigators in accordance with all applicable global laws and regulations.

8.0 STATISTICAL ANALYSIS PLAN

8.1 Statistical Analysis Plan Summary

The primary endpoint is laryngectomy-free survival (LFS) at 18 month. LFS for standard of care is approximately 70%; the trial hypothesis is that LFS at 18 month can be improved to at least 85% using the experimental agent. Forty seven patients are required to identify this improvement in 18 month LFS using a one-sided test with 10% significance and 80% power. This calculation is based on a non-parametric LFS distribution, and assumes that it will take 18 months to accrue all 47 patients, and that an additional 6 months of follow-up will be done after the last patient is enrolled.

Study size was calculated using the SWOG calculator for “one-arm nonparametric survival”: <http://www.swogstat.org/statoolsout.html>

8.2 Statistical Analysis Plan

Safety run-in phase: Although PD-1 inhibition is not expected to increase the toxicity of chemoradiation therapy, clinical trials of pembrolizumab combined with cisplatin and radiation for locally advanced head and neck carcinoma have not been conducted. In order to protect against unexpected problems a run-in safety analysis will be performed prior to completing the rest of the first stage of study. This safety analysis will occur after 6 analyzable patients are entered into study. Pembrolizumab will be administered initially at the recommended phase II dose of 200 mg q 3 weeks. If more than 2 dose-limiting toxicities (DLTs) in the cohort of 6 patients then pembrolizumab will be given subsequent to completion of chemoradiation. In the event of 0-2 DLT events, the study will proceed as planned. A DLT will be defined as a \geq grade 3 (CTCAE, v.4) adverse event that is definitely, probably, or possibly related to study drug, excluding grade 3 tumor flare and toxicities that are strongly associated with concurrent radiation and cisplatin (for example rash, mucositis, radiation dermatitis).

LFS will be estimated using the Kaplan-Meier method. The point estimate and standard error will be obtained from the Kaplan-Meier curve and a 95% confidence interval will be calculated to estimate 18-month LFS. A z-test will be used to test the primary hypothesis of improvement in 18- month LFS from 70% to 85%.

One-year LFS, Progression-free survival, overall survival, event-free survival, and patterns of failure will be estimated using the Kaplan-Meier method. Complete response at 3 months will be estimated with an exact 95% confidence interval. For correlative studies, prognostic factors for complete response will be identified using logistic regression analysis. Prognostic factors for outcomes will be identified using Cox proportional hazards analysis.

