2.0 TRIAL DESIGN

2.1 Trial Design

This study is an open label, single arm study which will enroll patients with locally advanced squamous cell carcinomas of the larynx. Positive tumor PDL1 expression by IHC will not be required for enrollment.

All patients will receive Pembrolizumab and cisplatin in combination with radiation. Pembrolizumab 200 mg flat dose given Q21 days will begin 3 weeks prior to initiation of chemoradiation and continued through the 21-day cycle until completion of chemoradiation. Cisplatin will be given 100 mg/m² every 21 days during radiation as per standard of care.

Pembrolizumab has well defined toxicities as single agent and has non-overlapping mechanisms of action with cisplatin and radiation. The safety of these agents used in combination has not been previously described, therefore the study will begin with a safety run-in phase 1 followed by the phase II design. See statistical section for details.

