2.1.1 Phase I run in

Both drugs are FDA approved for other disease indications, with safety and tolerability well described at the approved doses. Therefore the limited phase I portion of this study aims to assess the safety and tolerability of this drug combination at their established doses along with concurrent radiation. There will be no dose escalation cohorts within this phase I run in group.

The first six patients will constitute the phase I portion of this study. These initial 6 patients will be assessed for dose limiting toxicities (DLTs, defined in Section 2.1.1.1)

from the start of study treatment until the start of cycle #2 concurrent cisplatin/radiation and pembrolizumab. After these first 6 patients initiate cycle #1, enrollment to the study will be temporarily halted, and a formal DLT evaluation of all 6 patients will be conducted.

If ≤ 2 of these six patients experience DLTs after completion of cycle #1 concurrent cisplatin/radiation and Pembrolizumab, then the study will proceed to the phase II portion, using Pembrolizumab 200mg IV Q21 days and cisplatin 100mg IV each 21 day cycle.

If > 2 of these first 6 patients experience a DLT upon completion of cycle #1, the protocol will be amended to investigate use of pembrolizumab 200 mg IV Q 21 days subsequent to completion of chemoradiation. (3-6 weeks after last dose of radiation) (upon Merck approval)

Only upon completion of the DLT evaluation for these first 6 patients and the determination of appropriate Phase II dose, will enrollment reopen for the phase II expansion.

If toxicity results are unclear, we will allow 6 additional patients into Phase I portion (6 + 6). The second cohort will be assessed based on above definitions for DLTs. Unclear toxicity can include (but not limited to) adverse effects that are considered secondary to cisplatin or radiation and per protocol are not considered DLT (see section 2.1.1.1 for definition of DLT) , however, the investigator strongly feels they could be related to study drug or exacerbated by concurrent use of study drug and chemoradiation. This investigator initiated study will be under the oversight of the University of Cincinnati IRB and Data and Safety Monitoring committee.

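### The run-in go/no-go rule is stated twice, with different counting units and different DLT definitions, so the same six patients can pass under Section 2.1.1 and fail under Section 8.2

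*Combined protocol and SAP*

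**What the plan says.** **Section 2.1.1 (Phase I run in)** counts patients. The study proceeds if at most 2 "of these six patients experience DLTs after completion of cycle #1", and the protocol is amended if more than 2 "of these first 6 patients experience a DLT upon completion of cycle #1". For the definition it points twice to Section 2.1.1.1: patients are "assessed for dose limiting toxicities (DLTs, defined in Section 2.1.1.1"), and later "see section 2.1.1.1 for definition of DLT".

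**Section 2.1.1.1** takes related grade 3 or 4 non-hematologic toxicity. Among other things it excludes grade 3 immune-related events that return to grade 1 or less within 28 days. It then brings back pneumonitis, renal failure or nephritis, and AST, ALT or bilirubin elevation. It also lists toxicities to be attributed to pembrolizumab, such as grade 3-4 diarrhea/colitis, and sends other related grade 3-4 non-hematologic events to individual review.

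**Section 8.2** words the rule differently: "If more than 2 dose-limiting toxicities (DLTs) in the cohort of 6 patients then pembrolizumab will be given subsequent to completion of chemoradiation" and "In the event of 0-2 DLT events, the study will proceed as planned". It writes out its own definition, any related adverse event of grade 3 or higher, "excluding grade 3 tumor flare and toxicities that are strongly associated with concurrent radiation and cisplatin", the latter illustrated by rash, mucositis and radiation dermatitis. It does not refer to 2.1.1.1.

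**Section 2.1** introduces the run-in by sending the reader to the SAP: "the study will begin with a safety run-in phase 1 followed by the phase II design. See statistical section for details".

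**The concern.** A go/no-go rule should give one answer for any set of six patients. Here the threshold (2) and the cohort size (6) agree, but what is counted and what qualifies do not. The rule answers the phase I primary objective (Section 3.1.1), gates 41 further patients (Section 2.1.2), and determines whether pembrolizumab stays concurrent or is moved to follow chemoradiation. Someone working from Section 2 and someone working from 8.2 could report opposite run-in results. Choosing between the texts after the six patients' data have been seen is what a prespecified rule is meant to prevent.

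**Working it through.** The documents state no operating characteristics for the run-in, so there is no figure to reproduce. The check is a comparison of texts with counterexamples, followed by an illustration of size.

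**Counterexamples**

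| Six patients | Sections 2.1.1 and 2.1.1.1 | Section 8.2 as written |
|---|---|---|
| Two patients with three qualifying DLTs between them, four with none | 2 of 6 patients: go | 3 events: no-go |
| Three patients, each with one related grade 3 immune event that resolves within 28 days and is on neither the named exceptions nor the attribution list | 0 under the 28-day exclusion: go, unless individual review counts them | 3: no-go |
| Three patients, each with related grade 2 myasthenia gravis or Guillain-Barré syndrome | 3, because these are made DLTs within a grade 2-4 item, read literally: no-go | 0, below grade 3: go |

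The second and third rows hold even if 8.2 is read as counting patients. The hematologic difference matters less: 2.1.1.1 classes grade 3 or 4 myelosuppression as a cisplatin or radiation effect, and the open-ended exclusion in 8.2 could absorb it.

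**Size, counting unit only (8.2 read literally)**

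Assumptions: each patient has a DLT with probability p, and each DLT patient has one further DLT event with probability q. Decisions differ only when exactly two patients have a DLT and at least one of them has a further event:

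P(opposite) = P(K = 2) × [1 − (1 − q)²], with P(K = 2) = 15p²(1 − p)⁴.

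| p | P(K = 2) | q = 0.10 | q = 0.20 | q = 0.50 |
|---|---|---|---|---|
| 0.10 | 0.0984 | 0.0187 | 0.0354 | 0.0738 |
| 0.15 | 0.1762 | 0.0335 | 0.0634 | 0.1321 |
| 0.25 | 0.2966 | 0.0564 | 0.1068 | 0.2225 |

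For example, at p = 0.15 and q = 0.10: 0.1762 × (1 − 0.81) = 0.0335. Allowing only one further event per patient leaves out one patient with three events, so for a given p and q these figures are on the low side.

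**Size, definition only (patients counted under both texts)**

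Assumptions: p is the share of patients with a DLT under both texts, and d the share with a DLT under 8.2 only. The cases are nested, so

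P(go in Section 2, no-go in 8.2) = P(X ≥ 3 | 6, p + d) − P(X ≥ 3 | 6, p), with X binomial.

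| p | P(X ≥ 3), d = 0 | d = 0.01 | d = 0.02 | d = 0.05 | d = 0.10 |
|---|---|---|---|---|---|
| 0.10 | 0.0159 | 0.0047 | 0.0102 | 0.0315 | 0.0830 |
| 0.15 | 0.0473 | 0.0087 | 0.0182 | 0.0515 | 0.1221 |
| 0.25 | 0.1694 | 0.0161 | 0.0329 | 0.0863 | 0.1835 |

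The columns d = 0.01 and 0.02 stand for the reading in which the attribution list overrides the 28-day exclusion, so that only unlisted event types differ. The columns d = 0.05 and 0.10 stand for the reading in which the exclusion also covers listed types such as colitis. Section 2.1.1.1 does not say which reading is meant.

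**Reverse direction**

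Let e be the share of patients whose only event is grade 2 myasthenia gravis or Guillain-Barré syndrome, assumed 0.005 to 0.01. The same formula with e in place of d gives 0.0042 to 0.0087 at p = 0.15 and 0.0080 to 0.0161 at p = 0.25.

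**The case against.** The strongest reply has four parts.

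1. **Counting unit.** Section 8.2 probably means patients. It keeps the threshold and the cohort of six, and Section 5.9 also works per patient. This may well be right, and the counting-unit effect is then zero. But 8.2 does not say so, and the difference in definition remains.
2. **Definition gap.** It may be small. Listed immune toxicities may count under both texts, and unlisted ones go to individual review, which could count them too. The grade 2 myasthenia gravis or Guillain-Barré case rests on a literal reading of a carve-out from the cisplatin list. These points stand as limits on size. Yet 2.1.1.1 does not say whether its list overrides its own exclusion, nor whether a reviewed event enters the count.
3. **Precedence.** Section 2.1.1 points to 2.1.1.1 under a heading that names it as the definition. Against that, Section 2.1 sends the reader to the statistical section for the run-in, and 8.2 sets out a full definition there.
4. **Safeguards.** Enrollment halts for a formal evaluation, six more patients are allowed if toxicity is unclear, a no-go under 2.1.1 requires an amendment and the drug supplier's approval, and a DSMB monitors the trial. These reduce the risk of a hasty decision. None states which count or definition applies. The second cohort is judged by the Section 2 definitions and addresses unclear toxicity, not two clear but conflicting counts.

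**Conclusion.** The inconsistency is real and must be fixed. The definitions conflict on any reading of the word events in 8.2; the counting units conflict if 8.2 is taken as written. Most differences make 8.2 the stricter text, but not all.

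Over assumed patient DLT rates of 10% to 25%, opposite decisions arise in:

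- **Counting unit:** 1.9% to 22.2% of cohorts if 10% to 50% of DLT patients have a second event; zero if 8.2 means patients.
- **Definition, narrow reading:** 0.5% to 3.3%, shrinking towards zero if individual review counts the events.
- **Definition, wide reading:** 3.1% to 18.3%.
- **Reverse direction:** 0.4% to 1.6% (rates of 15% and 25% only).

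Every rate here is an assumption, because the documents give none; the contradiction depends on none of them. The phase II analysis of 18-month laryngectomy-free survival is not affected.

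**What to change.** Before the six-patient review:

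- Reconcile Sections 2.1.1, 2.1.1.1 and 8.2 to one DLT definition and one counting unit, stated in one place.
- Replace the restated rule and definition in 8.2 with a cross-reference. This also carries over the DLT window and the clause on events arising before cisplatin and radiation start, on which 8.2 is silent.
- In 2.1.1.1, state how the 28-day exclusion, the named organ exceptions, the pembrolizumab attribution list and individually reviewed events fit together, and from what grade myasthenia gravis and Guillain-Barré syndrome count.

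Which clinical rule applies is for the sponsor and investigator to decide. The change costs protocol and SAP wording only, with no extra patients or procedures.
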